## STATISTICAL ANALYSIS PLAN

**Estradiol Vaginal Cream USP, 0.01%**

**Protocol/Study Number 71759501**

endpoint will be conducted for supportive information.

### **Superiority to Placebo Analysis**

The mITT population and LOCF will be used to evaluate the superiority of both the Test and Reference products to Placebo.

Summary table with frequency and percentage on the proportion of responders by treatment group will be presented. If the proportion of Responders in the Test and the Reference product groups is numerically and statistically superior to that of the Placebo ( $p < 0.05$ ; using a two-sided CMH test, stratified by clinical site) then superiority of the Test and Reference products over Placebo will be concluded.

### **8.2.3 Treatment-by-Site Interaction and Pooling of Clinical Sites**

As this is a multiple-site study, the interaction of treatment-by-site may be evaluated for the primary efficacy endpoint in the PP population for equivalence testing. The treatment-by-site interaction will be evaluated by the Breslow-Day test for homogeneity of the odds ratio at the 5% significance level ( $p < 0.05$ , 2-sided). A site(s) with a low enrollment rate(s) may be pooled with its geographically closest site, so as to avoid bias in the stratification of the sites in the CMH test and in the estimation of a treatment-by-site interaction effect. The pooling will be done for low enrolling sites that account for less than 4-7% of the total number of patients in the PP population at the site with the highest enrolling rate in the PP population. If the treatment-by-site interaction term is found to be statistically significant ( $p < 0.05$ ) for the primary endpoint, then the interaction term will also be assessed for clinical relevance before pooling the data across sites. This will include examination of Responder rates at each site where sample sizes per treatment may be influential in the assessment of the interaction.

## **8.3 Safety Analysis**

### **8.3.1 Adverse Events**

All the AEs reported will be coded and classified according to the Medical Dictionary for Regulatory Activities (MedDRA) coding dictionary (Version 20.0 or higher). Each AE is to be evaluated for date of start and end, seriousness, severity, causal relationship with the study drug, action taken and outcome.

All AEs will be listed by patient and treatment.

The total number and percentage of patients with at least one AE, discontinued study drug due to AEs, AE severity, AEs related to investigational product, serious adverse events (SAEs), and death will be summarized by treatment groups.

## STATISTICAL ANALYSIS PLAN

**Estradiol Vaginal Cream USP, 0.01%**

**Protocol/Study Number 71759501**

A summary table of the number and percent of patients with AEs by system organ class, preferred term, and treatment group will be presented. Each patient will be counted only once within each preferred term.

A frequency summary table of the number of AEs by system organ class, preferred term, severity, and treatment group will be presented. Severity will be classified as “Mild”, “Moderate”, or “Severe”.

Similarly, a frequency summary table of the number of AEs by system organ class, preferred term, and relationship to a study drug, and treatment group will be presented. Relationship to a study drug will be classified as “Related” or “Not Related”.

Adverse event frequencies will be compared between treatments using the Fisher’s exact test.

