1.0 TITLE PAGE

Drug Product Estradiol Vaginal Cream USP, 0.01%

[figure not shown]
Population Approximately 535 postmenopausal females, 30-75 years of age inclusive, with moderate to severe vulvar and vaginal atrophy

Study Design A randomized, double-blind, placebo-controlled, multiple-site, parallel-design bioequivalence study with clinical endpoints

Sponsor Prasco LLC

Protocol/Study Number 71759501

Protocol Date 07/25/2017

CONFIDENTIAL PROTOCOL

A Randomized, Double-Blind, Placebo-Controlled, Parallel-Design, Multiple-Site Study to Evaluate the Therapeutic Equivalence of Estradiol Vaginal Cream, USP, 0.01% (Prasco LLC) to Estrace[®] Cream (Estradiol Vaginal Cream, USP, 0.01%) (Warner Chilcott) in the Treatment of Vulvar and Vaginal Atrophy, 71759501

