5.0 SYNOPSIS

Protocol Number	71759501
Title	A Randomized, Double-Blind, Placebo-Controlled, Parallel-Design, Multiple-Site Study to Evaluate the Therapeutic Equivalence of Estradiol Vaginal Cream USP, 0.01% (Prasco LLC) Compared to Estrace® Cream (Estradiol Vaginal Cream, USP, 0.01%) (Warner Chilcott) in the Treatment of Vulvar and Vaginal Atrophy.
Objectives	
The objectives of this study are to:
 
• Evaluate the therapeutic equivalence of a generic Estradiol Vaginal Cream USP, 0.01% (Prasco LLC) to the Reference product, Estrace® Cream (Estradiol Vaginal Cream, USP, 0.01%) (Warner Chilcott) in the treatment of vulvar and vaginal atrophy (VVA).• Demonstrate the superiority of the Test and Reference (active) treatments over Placebo (vehicle) treatment in patients with VVA.• Compare the safety of Test, Reference and Placebo treatments in patients with VVA.
Sponsor	Prasco LLC
Study Products	
• Test: Estradiol Vaginal Cream, USP, 0.01% (Prasco LLC)• Reference: Estrace® Cream (Estradiol Vaginal Cream, USP, 0.01%) (Warner Chilcott)• Placebo: Placebo (Test vehicle cream) Vaginal Cream (Prasco LLC) 
Study products will be supplied in tubes, with a calibrated plastic applicator for dose (2 grams) administration.

Dosage Regimen	Patients will be instructed to apply 2 grams study product to the treatment area once daily for seven days. Each patient is expected to receive seven doses.
Route of Administration	Intravaginal
Treatment Randomization	2:2:1 (Test: Reference: Placebo)
Patient Population	Approximately █ postmenopausal females, 30-75 years of age inclusive, with moderate to severe VVA.
Study Design	Randomized, double-blind, placebo-controlled, parallel-group, multiple-site bioequivalence study with clinical endpoints
Study Conduct	Eligible patients will be randomized in a 2:2:1 ratio to one of the three treatments (Test, Reference or Placebo). Following a 28-day screening

CONFIDENTIAL PROTOCOL

A Randomized, Double-Blind, Placebo-Controlled, Parallel-Design, Multiple-Site Study to Evaluate the Therapeutic Equivalence of Estradiol Vaginal Cream, USP, 0.01% (Prasco LLC) to Estrace[®] Cream (Estradiol Vaginal Cream, USP, 0.01%) (Warner Chilcott) in the Treatment of Vulvar and Vaginal Atrophy, 71759501

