8.5 Risks and Benefits

The risks and benefits to patients enrolled in clinical research studies that include a placebo treatment group must be carefully considered based on three main criteria, namely: the disease being treated, the availability, efficacy and safety of already approved therapies, and the scientific and statistical requirements of the desired outcome of the research study. The Office of Human Rights Protection (OHRP), a Division of the USA Federal Government's Department of Health and Human Services,

CONFIDENTIAL PROTOCOL

A Randomized, Double-Blind, Placebo-Controlled, Parallel-Design, Multiple-Site Study to Evaluate the Therapeutic Equivalence of Estradiol Vaginal Cream, USP, 0.01% (Prasco LLC) to Estrace[®] Cream (Estradiol Vaginal Cream, USP, 0.01%) (Warner Chilcott) in the Treatment of Vulvar and Vaginal Atrophy, 71759501

has issued a detailed guidebook to Institutional Review Boards (IRBs) that includes discussion on the use of placebos in clinical studies.¹⁷

Qualified patients have a 20% chance they may be randomized to Placebo. Randomized patients will be enrolled in the study for 8 or 9 days. Although the potential for any drug-related side effects of significance occurring during the study are low, the risk is higher in the two active treatment groups than in the Placebo group.

All patients enrolled in this study will receive the benefit of free specialized medical care beyond standard medical treatment that would be expected through most health insurance plans. In addition, the patient will receive a stipend for participation to cover costs and expenses associated with trips to the medical facility.

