### **Safety Population**

The safety population will include all patients who are randomized and received study product.

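### The two adverse event tables that split preferred terms by severity and by relationship count events rather than women, so under 2:2:1 allocation they cannot be compared directly between arms

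*SAP*

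**What the plan says.** SAP 8.3.1 describes four adverse event summaries.

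1. An overall summary per woman, which opens with "The total number and percentage of patients with at least one AE" and goes on to cover severity, relatedness, serious events, death and discontinuation of study drug. It is not split by preferred term.
2. A table by system organ class and preferred term giving number and percent of patients, each counted once within a term. It has no severity or relationship.
3. A table by severity within preferred term: "A frequency summary table of the number of AEs by system organ class, preferred term, severity, and treatment group will be presented".
4. A table by relationship: "Similarly, a frequency summary table of the number of AEs by system organ class, preferred term, and relationship to a study drug, and treatment group".

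The text for tables 3 and 4 mentions no percentage, no denominator and no once-per-patient rule. All events are also listed by patient and treatment.

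The SAP defines the denominator that per-woman tables would use: "The safety population will include all patients who are randomized and received study product". Protocol 5.0 (Treatment Randomization) gives the allocation as "2:2:1 (Test: Reference: Placebo". Comparing safety across the three arms is the third study objective in both documents. Protocol 11.7 asks for tables comparing incidence, severity and relationship, among other features, by treatment group. It does not say that severity or relationship must be shown per woman within a preferred term.

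**The concern.** Tables 3 and 4 are the only planned summaries that cross the type of event with its severity or its relationship to study drug. Their unit is the event, and the Placebo arm has half as many women as each active arm. A reader comparing the counts across columns would see more events on the active arms when risk is equal.

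What is lost is a specific set of figures: the percentage of women in each arm who had a severe event of a given term, and the percentage who had a related one. These are natural questions for a locally applied cream. The Reference label in Protocol Appendix C lists application site burning and irritation among its adverse reactions, and a reviewer may ask how many women per arm had such an event judged related.

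**Working it through.** **Inputs**

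- Allocation 2:2:1 (Protocol 5.0).
- Planned size: "Approximately 535 postmenopausal females, 30-75 years of age inclusive" (Protocol title page).
- Stated chance of Placebo: "Qualified patients have a 20% chance they may be randomized to Placebo" (Protocol 8.5).
- Assumptions: all 535 women are dosed and so enter the safety population. The event risks below are illustrative, since the documents give none. One event per affected woman is assumed unless stated.

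**Step 1: reproduce the plan's figure.** Placebo share = 1/(2 + 2 + 1) = 0.20, which agrees with the stated 20%.

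**Step 2: arm sizes.** Test and Reference: 535 × 2/5 = 214 each. Placebo: 535 × 1/5 = 107.

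**Step 3: expected counts at equal risk.** Take one cell of table 3 or 4, such as severe events of one term, or related events of one term. Let r be the expected number of events per woman in that cell, equal in all arms. Expected counts are 214r, 214r and 107r, and the active-to-Placebo ratio is 214r/107r = 2.0 whatever r is.

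| Assumed r | Each active arm | Placebo |
|---|---|---|
| 2% | 4.3 | 2.1 |
| 5% | 10.7 | 5.4 |
| 10% | 21.4 | 10.7 |
| 20% | 42.8 | 21.4 |

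**Step 4: how often a given active arm shows the larger count at equal risk.** With one event per affected woman, P = Σₓ P[Bin(107, p) = x] × P[Bin(214, p) > x]. This is 0.74 at p = 2%, 0.90 at 5% and 0.97 at 10%. The factor of two is therefore an average and not what every sample will show, particularly in sparse cells.

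**Step 5: the converse.** If the cell risk were 5% on an active arm and 10% on Placebo, expected counts would be 214 × 0.05 = 10.7 and 107 × 0.10 = 10.7. A twofold difference in risk would show as equal counts.

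**Step 6: what each planned summary gives.**

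| Quantity, per arm | Where it is planned |
|---|---|
| % of women with any AE, by severity, or with a related AE, over all terms | Table 1 |
| % of women with a given term | Table 2 |
| Number of events of a given term, by severity | Table 3 |
| Number of events of a given term, by relationship | Table 4 |
| % of women with a severe event of a given term | No summary described |
| % of women with a related event of a given term | No summary described |

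The last two rows cannot be derived from the rows above. Table 2 gives the women but not their severity or relationship, and tables 3 and 4 give the events but not the women.

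**Step 7: the same cells counted per woman.** At an equal 5% risk the three arms would read 5%, 5% and 5%, where the event counts read about 10.7, 10.7 and 5.4.

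**The case against.** The strongest answer is that most of this is already handled in the same SAP section. Table 2 gives the incidence of each term per woman with percentages, and table 1 gives severity and relatedness per woman overall. The by-patient listing lets anyone count the missing figures. A reader who knows the arm sizes can rescale the event counts. Within an arm, the split of events by severity does not depend on arm size. Event counts shown beside patient percentages describe a different quantity and are not wrong in themselves. No stated decision rule uses tables 3 and 4. All of this stands, and it reduces the point to two descriptive tables. Rescaling gives events per woman, however, and this equals the percentage affected only if no woman has two events in the same cell.

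The shells in SAP section 9 are redacted. They may show arm sizes or percentages, so the point rests on the SAP text. Even then, the unit the text specifies is the event.

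A reader might infer three stronger things that the documents do not support.

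- *That the plan lacks a per-woman comparison of adverse events, or that the ordering of the arms for a whole term could be reversed.* Table 2 reports whole-term incidence per woman and would show the right ordering.
- *That one woman with a reaction on each of seven days would outweigh several others.* This needs each day to be entered as a separate event. No such rule is given. Women are asked about changes since the last visit, and each event has a start and an end date, which fits a single continuing entry at least as well. Signs and symptoms of the disease itself, which include irritation and itching, are generally not recorded as adverse events (Protocol 11.7).
- *That one woman's severity and causality could be read together after a change to patient counts.* Two separate tables still would not give, for example, moderate or severe events that were also related.

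**Conclusion.** The point holds in a narrow form. As worded, SAP 8.3.1 makes the two tables by preferred term with severity or relationship counts of events. With arms of about 214, 214 and 107, equal risk gives on average a twofold difference in those counts, so they do not support a direct comparison between arms. The percentage of women with a severe, or a related, event of a given term is given in no summary the text describes.

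The factor of two depends only on the allocation and on similar proportions of women being dosed in each arm. The probabilities of 74% to 97% further assume risks of 2% to 10% in a cell and one event per affected woman. Whether repeat reactions become separate entries is not settled by the documents, and the conclusion does not depend on it.

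The equivalence and superiority conclusions rest on the efficacy endpoints and are unaffected. This is an inexpensive improvement to safety reporting under the third objective. It does not expose a fault in the trial's conclusions.

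**What to change.** In SAP 8.3.1, change the counting rule for both tables:

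- Severity table: count each woman once per system organ class and preferred term, at her worst severity.
- Relationship table: count each woman once per system organ class and preferred term, as Related if any occurrence was related and otherwise as Not Related.
- In both, show n and % of the safety population in each arm, and keep the number of events as an additional column so that repeat events remain visible.
- If severity among related events is wanted, repeat the severity table for related events only.

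No new data are needed. The cost is a short wording change, edits to two table programs and their shells, and slightly wider tables. The optional repeat adds one more output.

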11.7 Safety Analysis

Adverse events will be classified using standard MedDRA terminology Version 20.0 or higher and summarized by treatment group. Summary tables comparing the type, incidence, date of onset, date of resolution, severity, action taken, outcome and Investigator’s opinion of relationship to the study product will be prepared by treatment group. If sufficient data exist, AE frequencies will be compared between treatments using Fisher’s exact test or a similar test.

Signs and symptoms of VVA will not be considered AEs, unless in the Investigator’s opinion, they have increased in frequency and/or severity to such an extent that the Investigator/patient considers that it is in the patient’s best interest to be dropped from continued participation in the study and given alternative therapy for their condition.

Concomitant medication use during the study will be tabulated by patient.

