### **2. OBJECTIVES**

The objectives of this study are to:

1. Evaluate the therapeutic equivalence of a Test product, the generic Estradiol Vaginal Cream USP, 0.01% (Prasco LLC) to the Reference product, Estrace® Cream (Estradiol Vaginal Cream, USP, 0.01%) (Warner Chilcott) in the treatment of VVA.
2. Demonstrate the superiority of the active treatments (Test and Reference) over Placebo (vehicle) treatment in patients with VVA.
3. Compare the safety of Test, Reference and Placebo treatments in patients with VVA.

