## **8. STATISTICAL ANALYSIS METHODS**

If not otherwise specified, statistical significance is defined as  $p < 0.05$  and is two-tailed. Data will be summarized with respect to demographic and baseline characteristics, efficacy variables and safety variables.

For categorical variables, the number and percent of each category within a parameter will be calculated for non-missing data. For continuous variables, statistics will include n, mean, standard deviation, median, minimum and maximum values.

All statistical analyses will be conducted using SAS®, [REDACTED]

[REDACTED]  
[REDACTED]  
[REDACTED]

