### **8.4 Multiple Comparisons**

No multiple comparison adjustment will be made in this study.

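### The readable plan gives no between-arm safety difference or confidence interval, only Fisher p-values, which cannot show similar safety for low-incidence adverse events

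*SAP*

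**What the plan says.** The third objective in SAP section 2 is: "Compare the safety of Test, Reference and Placebo treatments in patients with VVA". Protocol section 9.0 has the same objective.

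SAP 8.3.1 plans, by treatment group, the number and percentage of patients with any AE, discontinuation due to AEs, related AEs, serious AEs and death. It also plans tables by system organ class and preferred term, by severity and by relationship. The only between-arm method follows: "Adverse event frequencies will be compared between treatments using the" Fisher's exact test. The text does not say whether the test is pairwise or three-arm, or whether it applies to overall incidence or to each term.

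Protocol 11.7 and its Synopsis copy are more tentative: "If sufficient data exist, AE frequencies will be compared between treatments using" Fisher's exact test or a similar one.

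The significance level comes from the SAP section 8 default. "If not otherwise specified, statistical significance is defined as" p < 0.05 "and is two-tailed". SAP 8.4 adds: "No multiple comparison adjustment will be made in this study". Vital signs (SAP 8.3.2) are descriptive only.

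**The concern.** A test of difference answers whether the arms can be told apart. It does not say how large a difference remains compatible with the data. For efficacy the plan respects this distinction: Test and Reference are compared through a 90% confidence interval held against ±20 percentage points. For safety, the readable text offers only the difference test.

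The arm sizes were not chosen for safety. The sample-size sections name only efficacy equivalence and superiority on the primary endpoint. If an AE is uncommon, a real excess on one arm could easily give p > 0.05, and the planned inferential output would not show how large an excess is still possible. The Reference label in Protocol Appendix C lists application-site burning and irritation, genital pruritus and vaginitis, so local tolerability is a natural question for the Test v Reference comparison.

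**Working it through.** **Inputs.**
- Total N: "Approximately 535 postmenopausal females, 30-75 years of age inclusive" (Protocol title page).
- Allocation: 2:2:1 (Protocol Synopsis). 535 × 2/5 = 214 for Test and for Reference; 535 × 1/5 = 107 for Placebo.
- Safety population: all women randomised who received product. I assume nearly all are dosed.
- Level: two-sided 0.05, unadjusted (SAP 8 and 8.4). I assume pairwise tests.
- AE rates: none in the documents, so they are varied.

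The 535 cannot be rebuilt because its assumptions are redacted. There is no stated safety power to reproduce.

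**Power.** For arms of size n₁ and n₂ with true rates p₁ and p₂, exact power is the sum of Bin(x; n₁, p₁) × Bin(y; n₂, p₂) over all tables (x, y) whose two-sided Fisher p-value is below 0.05. The active arm carries the higher rate in the Placebo comparison.

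| Doubling | Test v Reference (214/214) | Active v Placebo (214/107) |
|---|---|---|
| 2% to 4% | 14% | 8% |
| 5% to 10% | 44% | 28% |
| 6% to 12% | 53% | 35% |
| 8% to 16% | 68% | 49% |
| 10% to 20% | 80% | 62% |
| 15% to 30% | 95% | 84% |
| 20% to 40% | 99% | 96% |

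Power for a doubling reaches 50% at a lower rate of about 5.75% for Test v Reference (50.5% at 5.75%). For active v Placebo it does so just above 8% (49.5% at 8%, 51.2% at 8.25%). With 200/200/100 dosed, power is 49% at 6% to 12% (Test v Reference) and 47% at 8% to 16% (active v Placebo).

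At a 5% comparator rate, 80% power for Test v Reference needs about 13.0% in the other arm (79.8% at 13.0%, 83.9% at 13.5%).

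Increases smaller than a doubling are harder to detect. For Test v Reference, 10% v 15% has 30% power and 20% v 30% has 63%.

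**Illustration.** Suppose 20/214 on Test and 11/214 on Reference.
- Rates are 9.35% and 5.14%, a difference of 4.21 points. Fisher p = 0.135.
- Wilson 95% limits are 6.13% to 13.99% and 2.89% to 8.97%.
- Newcombe lower limit: 4.21 − √[(9.35 − 6.13)² + (8.97 − 5.14)²] = 4.21 − 5.00 = −0.8.
- Newcombe upper limit: 4.21 + √[(13.99 − 9.35)² + (5.14 − 2.89)²] = 4.21 + 5.16 = +9.4.

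The p-value alone reads as not significant. The interval shows that an excess of up to about 9 points has not been excluded.

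**What an interval would give.** The approximate half-width at equal true rates is 1.96 × √[p(1 − p)(1/n₁ + 1/n₂)]. For Test v Reference at 5% this is 1.96 × √[0.0475 × 2/214] = 4.1 points, and at 10% it is 5.7. For active v Placebo the values are 5.1 and 7.0.

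**The case against.** A reader might go further than the documents allow in four ways.

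- **That the test misses a doubling more than half the time.** This depends on the baseline rate, which the documents do not give. It fails above about 5.75% for Test v Reference and above about 8% for active v Placebo. Overall any-AE incidence could fall on either side.
- **That no safety estimate is planned.** Per-arm counts and percentages are planned in some detail. A reader could form each difference from them, and with the arm sizes an interval. What is missing is a pre-specified between-arm contrast with its interval.
- **That a non-significant result would be taken as the answer to objective 3.** No text says so. The objective is to compare, not to demonstrate comparability, and arm-by-arm tables are a comparison. There is no safety margin or pass/fail rule, equivalence rests on the primary efficacy endpoint alone, and the protocol makes the Fisher test conditional on sufficient data.
- **That the Test cream has a different base, and so a known tolerability risk.** The readable text lists excipients only for the Reference.

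The table shells are also unreadable, so intervals may be shown there.

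These objections limit the claim but do not remove it. The method text should still specify the contrast, because a Fisher p-value is the only between-arm inference it names, and individual preferred terms may well lie in the low-incidence range where power is poor.

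**Conclusion.** The point holds in a limited form. The readable SAP and protocol text plans per-arm AE summaries and Fisher's exact test, with no between-arm safety difference or interval, although comparing safety is a stated objective. For low-incidence AEs, a p-value above 0.05 would not show similar safety: power for a doubling is under about 50% when the lower rate is below about 5.75% (Test v Reference) or 8% (active v Placebo). For commoner events the test does better, with 80% and 62% power at 10% v 20%.

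These figures rest on nearly all of about 535 women being dosed at 2:2:1, pairwise testing, and assumed AE rates. The equivalence and superiority decisions are unaffected. This is an inexpensive improvement to how objective 3 is answered.

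**What to change.** In SAP 8.3.1, replace the single Fisher sentence with text to this effect:

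> For the proportion of patients in the safety population with at least one AE, at least one related AE, at least one vulvovaginal or application-site AE, and discontinuation due to an AE, the risk differences Test − Reference, Test − Placebo and Reference − Placebo will be reported with two-sided 95% Newcombe score confidence intervals. Fisher's exact p-values, if shown, are descriptive. A p-value above 0.05 will not be taken as evidence of comparable safety; conclusions on objective 3 will be stated from the confidence limits.

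Make the matching change in Protocol 11.7 and the Synopsis. If the shells already contain such intervals, the method text need only be brought into line with them.

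The cost is SAP and protocol wording and a few extra table columns, with no new data or patients. The downside is that the intervals will show that moderate excesses cannot be excluded, so the safety statement becomes somewhat less favourable.
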